2.2.2 Results (See publications [128,129])

Enrollment: A total of 82 subjects were enrolled into 6 ALB dose-tiers. Enrollment of the last subject into the final dose-tier, Tier VI, occurred on May 1, 2005.

Demographics: The following demographics describe the 82 subjects enrolled in Tiers I through VI:

5.3.1	Mean age (\pm SD)	65.2 \pm 14.9 years; range: 25-88 years
5.3.1	Gender	Male, 43 (52%); Female, 39 (48%)
5.3.1	tPA use	tPA, 42 (51%); Non-tPA, 40 (49%)
5.3.1	Ethnic origin	Non-Hispanic Caucasian, 60 (73%)
5.3.1		Hispanic, 9 (11%)
5.3.1		African-American, 9 (11%)
5.3.1		Native American, 1 (1%)
5.3.1		Asian, 1 (1%)
5.3.1		Other, 2 (2%)

[figure not shown]
Safety Considerations -- Non-Serious Adverse Events: The only adverse events bearing a relationship to ALB therapy (comprising “unlikely”, “possible”, “probable”, or “definite”) were those related to intravascular volume expansion: i.e., shortness of breath and frank pulmonary edema / congestive heart failure in the hours or days following ALB administration. At Dose Tiers I and II, these adverse events were only rarely observed. At Dose Tier III, the cardiologists on the SEC suspected that we were beginning to enter a dose range which produced evidence of mild pulmonary congestion, at least in elderly subjects with altered ventricular compliance or pulmonary systolic hypertension. For this reason, we proposed to the DSMB that the protocol be modified to require chest x-rays at both 24 hours and 48 hours after ALB administration, and the DSMB approved this modification. Furthermore, we proposed to measure brain natriuretic peptide (BNP) to compare levels prior to ALB therapy, and 24 hours after therapy, The BNP levels may be sensitive to incipient cardiac failure related to ALB administration. After 12 subjects were recruited at Dose Tier IV, a second set of 6 subjects was requested by the DSMB. At Dose Tier IV, out of a total of 18 subjects, a consensus of SEC members noted chest x-ray evidence of pulmonary / CHF in 4 subjects. In another 3 subjects, similar changes were noted by 1 or 2 of the 6 SEC members. Of the 18 subjects in Dose Tier IV, clinical evidence of pulmonary edema was noted by SEC members in 5 subjects. In 3 of these 18 subjects, SEC members noted the use of diuretics.

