Twelve subjects were studied in Dose Tier V. Of these, the SEC noted that very mild clinical symptoms of pulmonary congestion/edema occurred in 2 subjects, one of whom also had chest x-ray changes. Prophylactic furosemide was administered in 4 of these 12 subjects.

Twelve subjects were enrolled in the final dose-tier, Tier VI (2.05 g/kg). One subject developed clinical and chest x-ray signs of mild pulmonary edema, which was easily managed with 2

doses of furosemide. None of the other 11 Tier-VI subjects received furosemide. SEC members noted that four subjects of Tier VI showed mild interstitial edema on chest x-ray without clinical findings.

[figure not shown]
5.3.1

Physiological Aspects: Overall, ALB administration was well tolerated without important alterations of these variables, except for plasma albumin level itself, and hematocrit (See figures above, which present data from Tiers I-VI.)

[figure not shown]
The plasma albumin levels prior to ALB administration averaged 3.8 g/dl. ALB infusion led to a dose-related increase in plasma albumin levels, most marked at 4 hours post-infusion and declining to pre-infusion levels by 48-72 hours. In Dose Tier VI, the increase at 4 hours averaged 2.0 g/dl above baseline. Correspondingly, ALB administration produced a dose-dependent hemodilution, maximal at 4-12 hours but still present at 48h post-infusion. In Tier VI, the decrease in hematocrit at 4 hours averaged 9.8 points (23%) below the pre-infusion values.

Plasma BNP, was measured in subjects of Tiers IV, V, and VI prior to ALB infusion (n=40) and 24 hours later (n=38). Elevated BNP levels are thought to reflect increased cardiac filling pressure

[80]. In all subjects, BNP levels rose post-ALB infusion, and subjects' age was highly correlated with BNP, both at baseline and post-ALB infusion (See figure above). However, there was no correlation between BNP (either pre- or post-ALB infusion) and initial stroke severity (NIHSS score). Interestingly, there was also *no correlation* between the extent of BNP increase and the presence or absence of cardiac adverse events. The extent of increase in plasma BNP levels post-ALB did not differ between subjects with vs. without cardiac adverse events.

[figure not shown]

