5.3 Concomitant Interventions

5.3.1 For Both Thrombolysis and Non-Thrombolysis Subjects

According to the principle of the ALIAS Trial as a large simple trial of ALB compared to placebo over and above the best standard of care, few restrictions on concomitant care are made. However, one exception is that fluid management procedures and diuretic use mandates must be followed.

Mandatory

Fluid Management: Subjects shall receive no additional intravenous fluid during infusion of study drug with the exception of standard IV thrombolysis. IV thrombolysis should be given, if appropriate, through a dedicated IV catheter. After completion of study drug infusion (2 hour +/- 15 min.), the subject may receive no more than 75 cc/h of IV fluid for the next 46 hours. Normal saline (0.9% NS) is the preferred IV solution since glucose may promote worsening of ischemic brain injury. The total intravenous fluid received in the first 48 hours of care should not exceed 4200ml (~600 ml study drug + 75ml/h 0.9% NS + 90 ml thrombolysis = 4140 ml). Note that obese or large subjects >100 kg may receive 4290 ml according to the same formula. Strict ins (IV fluids only) and outs should be measured for the first 48 hours of a subject's care. There may be situations where additional fluid

is required because of a subject's condition (e.g., shock or hemorrhage). Any exceptions made to the fluid administration mandate must be documented in the CRF.

Diuretics: In general, stroke patients should be treated aiming for euvolemia. One potential complication of ALB infusion is volume overload with subsequent pulmonary congestion. Diuretics may be used in the acute phase to promote diuresis to allow subjects to better compensate for an episode of pulmonary congestion. Loop diuretics such as furosemide are preferred because they act quickly and can be administered intravenously. A single dose of furosemide, 20 mg IV, (or an equivalent loop diuretic such as ethacrynic acid) should be administered as a routine standard-of-care between 12 and 24 hours after the start of study drug administration. If the treating physician chooses not follow this treatment guideline, the reason for withholding diuretic must be documented in the case report form. From the time of treatment through 24 hours, all subjects are evaluated for evidence of respiratory compromise due to congestive heart failure.

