Recommended Best Care: Over the first 7 days of in-patient care, subjects' cardio-respiratory status should be reviewed with particular care. It is over this time period that ALB will redistribute in the body and exert an oncotic effect. Close continued attention to the fluid balance, and cardiac status is required. Treating neurologists should have a low threshold to promote diuresis during the acute hospital stay.

Antiplatelet/anticoagulant therapy: Antiplatelet therapy should be administered to all subjects within 48 hours of their stroke. Aspirin (ASA, acetylsalicylic acid), 81-325 mg daily (low dose) is the preferred drug. Subjects who are naïve to ASA may be loaded with 160 mg ASA on the first day of their dosing. Subjects who receive IV thrombolysis should not be treated with ASA until 24 hours after thrombolysis therapy, and after a 24-hour neuroimaging procedure shows no evidence of intracranial hemorrhage. Subjects who are hypersensitive to ASA may receive clopidogrel. Combined ASA and dipyridamole (Aggrenox™) is an acceptable alternative to ASA or clopidogrel. Ticlopidine is not an acceptable alternative to ASA because of known hematologic toxicity.

Anticoagulation: Anticoagulation with heparin is discouraged. There is no general evidence that heparin is useful in the acute management of stroke subjects for any stroke type. Low-dose subcutaneous unfractionated heparin or low molecular weight heparin may be given after 24 hours, to prevent deep venous thrombosis/pulmonary thromboembolism.

Blood pressure reduction: Blood pressure may be treated according to the local standards of the clinical sites and the standards for thrombolysis treatment. According to the principle of this Trial, whose goal is to assess ALB therapy over and above standard-of-care, no restrictions on blood pressure are in place prior to ALB/placebo therapy. Blood pressure and blood pressure treatments in the acute phase must be recorded.

Glucose-lowering therapy (insulin): Currently, there are no completed controlled trials to suggest that lowering glucose in the acute phase results in improvements in clinical outcome among acute stroke subjects. However, subjects with myocardial infarction and critically ill subjects may benefit from aggressive glucose control [77]. Elevated glucose is associated with a higher rate of symptomatic intracranial hemorrhage after thrombolysis therapy [27,104]. Risk factors for

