Adverse events are further graded as mild, moderate, severe, life-threatening, or fatal. Adverse events that are non-serious must be followed through the 3-month follow up visit. Only serious adverse events are reported beyond the 3-month follow up visit.

An **unexpected adverse event** is any event for which the specificity or severity is not consistent with the current investigator brochure; or, an adverse event for an individual subject that may be adjudicated to be “unexpected” in view of the severity, the timing, and/or the medical context in which it occurs. The study site PI should take all factors carefully into account in deciding whether he/she believes that the event is expected or unexpected.

A **Serious Adverse Event (SAE)** is one that results in any of the following outcomes:

- death due to any cause;
- a life-threatening adverse experience (i.e., the subject was at immediate risk of death from the event as it occurred);
- in-patient hospitalization or prolongation of existing hospitalization. (Hospitalizations scheduled before enrollment for an elective procedure or treatment of a pre-existing condition that has not worsened during participation in the study is not considered a serious adverse event);
- a persistent or significant disability/incapacity (i.e., a substantial disruption of one’s ability to conduct normal life functions);
- a congenital anomaly/birth defect;
- an important medical event that may not result in death, be life-threatening, or require hospitalization, but may jeopardize the subject and may require medical or surgical intervention to prevent one of the outcomes listed in this definition. Any new diagnosis of cancer (made after study enrollment) is considered an important medical event.

For the ALIAS Trial, **severe, or life-threatening** pulmonary edema or CHF (as defined in Section 8.2) occurring within 48 (\pm 6) hours of randomization is considered a SAE. All serious adverse events must be followed for the duration of the 12-month trial or until resolution, whichever comes first.

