8.2 Formal Definitions of Selected Adverse Events

Acute Congestive Left Heart Failure/Pulmonary Edema. Acute CHF is defined as pulmonary edema occurring within 48 (\pm 6) hours of randomization. Pulmonary edema is characterized by all of the following: (a) supplemental oxygen requirement or an increase in oxygen requirement with associated fall in SaO₂; (b) elevated respiratory rate and tachycardia; (c) physical examination evidence of pulmonary congestion including elevated jugular venous pressure, presence of hepatjugular reflux, pulmonary auscultatory rales or wheezing.

Although a CXR is not required for diagnosis, if one is done and shows radiological evidence of pulmonary edema it will support the diagnosis.

Acute CHF/pulmonary edema is further classified as:

- (i) Asymptomatic – the subject requires no additional therapy. Pulmonary congestion may be only shown on CXR in this case.

- (ii) Mild – the subject requires and responds to the single mandated dose of a diuretic and requires supplemental oxygen via nasal prongs only. A single dose of diuretic shall be considered 20mg of intravenous furosemide.
- (iii) Moderate – the subject requires more than the mandatory dose of a diuretic but responds and requires supplemental oxygen via nasal prongs only.
- (iv) Severe – the subject requires treatment with multiple doses of diuretic, supplemental oxygen via face mask, or additional problems arise such as cardiac arrhythmias and cardiac telemetry is required.
- (v) Life-threatening – the subject requires intubation or non-invasive BiPAP/CPAP to manage significant hypoxemia.

Acute coronary syndrome (MI). Elevated cardiac-specific CK (total CK-MB mass), troponin-T, or troponin-I greater than the upper limit of normal (ULN) at the clinical site **plus** clinical symptoms or EKG evidence of myocardial injury (ST deviation ≥ 1 mm in 2 contiguous leads or new/previously undocumented Q waves). [120]

Myocardial injury without acute coronary syndrome -- “enzyme leak”. Elevated cardiac-specific CK (total CK-MB mass), troponin-T, or troponin-I greater than the upper limit of normal (ULN) at the clinical site in the absence of clinical symptoms or EKG evidence of an acute coronary syndrome.

Acute coronary syndrome - unstable angina. Clinical symptoms (chest pain, dyspnea) or EKG evidence (ST depression or T wave inversion) of reduced myocardial flow without a significant elevation in cardiac enzymes. [120,121]

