8.8 Monitoring of Specific Adverse Events

Incidences of the following specific adverse events are monitored by the Trial EC in a blinded manner and by the unblinded Trial personnel and the DSMB by treatment group throughout the study:

- Neurological deterioration as assessed by the investigator of an increase of 4 points or more on the NIHSS anytime within 48 (\pm 6) hours of randomization
- Neurological death from stroke during hospitalization or within 7 days (\pm 6 hours) of randomization, whichever is shorter
- Recurrent stroke within 30 (\pm 7) days of randomization
- Atrial fibrillation within 48 (\pm 6) hours of randomization
- Severe or life threatening pulmonary edema or CHF within 48 (\pm 6) hours of randomization
- Shortness of breath within 48 (\pm 6) hours of randomization
- Symptomatic ICH within 24 (\pm 6) hours of randomization
- Asymptomatic ICH as assessed by the CT scan at 24 (\pm 6) hours
- Death from any cause within 30 (\pm 7) days of randomization
- Death from any cause within 90 (\pm 14) days of randomization

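### The definition, grading, automatic SAE rule and by-arm count for pulmonary edema/CHF stop at 48 (±6) hours, although the protocol describes albumin's oncotic effect as running through the first 7 days

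*Protocol*

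**What the plan says.** **The event window.** Three linked parts of the protocol use 48 (±6) hours from randomization.

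- Section 8.2: "Acute CHF is defined as pulmonary edema occurring within 48" (±6) hours of randomization. A five-level grading, from asymptomatic to life-threatening, follows under that definition.
- Section 8.1: an episode is an SAE by trial-specific rule if it is severe or life-threatening "pulmonary edema or CHF (as defined in Section 8.2) occurring within 48" (±6) hours.
- Section 8.8, the list that the DSMB and unblinded personnel follow by treatment group: "Severe or life threatening pulmonary edema or CHF within 48" (±6) hours, and "Shortness of breath within 48" (±6) hours.

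**The risk period.** Elsewhere the protocol describes a longer or less sharply bounded period.

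- Section 5.3.1 asks for careful cardio-respiratory review over the first 7 in-patient days, because "It is over this time period that ALB will redistribute in the body and exert an oncotic effect".
- Section 2.2.2 describes the albumin-related events of Phase I as "shortness of breath and frank pulmonary edema / congestive heart failure in the hours or days following ALB administration".
- Section 2.2.2 also describes hemodilution as "maximal at 4-12 hours but still present at 48h post-infusion", and says plasma albumin peaked at 4 hours and was back at its pre-infusion level by 48-72 hours.
- Section 5.3.1, on fluids after the 2-hour infusion: "the subject may receive no more than 75 cc/h of IV fluid for the next 46 hours".

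**The concern.** Volume overload is the harm the investigators expect from the drug's mechanism. A reader would expect the purpose-built count of that harm to cover the period over which the protocol says the mechanism operates. It stops well before that, and no reason is given. It also stops at about the time the cap on intravenous fluid is lifted (2 + 46 = 48 hours from the start of infusion).

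What is at stake is comparability. A pulmonary edema episode on Day 4 or 5 enters the database as an ordinary adverse event, named and graded at the site's discretion. An episode at 40 hours is held to a written definition and a five-level scale. A DSMB that wants the arms compared on this harm after 48 hours has no line built for it.

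**Working it through.** The point rests on setting sections side by side; the protocol gives no figure to reproduce.

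**1. Share of the stated risk period covered.** Stated period: 7 × 24 = 168 h.

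| End of window | Share of 168 h |
|---|---|
| 42 h | 42/168 = 25% |
| 48 h | 48/168 = 29% |
| 54 h | 54/168 = 32% |

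The clocks differ slightly. The event window runs from randomization, the fluid cap from the end of infusion, and the 7-day statement refers to in-patient care. These offsets do not change the picture. The shares are shares of time, not of events.

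**2. What happens to an episode with onset on Day 4.**

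- Section 8.2: it is not acute CHF, so on a plain reading the CHF-specific grading does not apply. The general AE grades of 8.1 remain.
- Section 8.1: it is not an SAE by the trial-specific rule, but it is one if it meets a general criterion, such as being life-threatening or prolonging hospitalization.
- Section 8.8: it is outside both the CHF item and the shortness-of-breath item.
- Section 8.4: it is recorded, since non-serious AEs are collected to 3 months and SAEs to 12 months.
- Sections 8.7 and 10.7.3: it reaches the DSMB through aggregate AE reports and safety reports by coded arm.

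The loss is therefore from the defined, graded, named count, not from the database.

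**3. Can the size be computed?** Let f be the share of episodes that start after the window. If f is the same in both arms, the observed rates are p(1−f). The absolute difference shrinks by the factor (1−f) and the ratio is unchanged. The ratio moves only if f differs between arms. The protocol gives neither f nor the underlying rates.

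To show how far the answer depends on assumptions, take 550 per arm (1,100/2), a two-sided 5% comparison and equal f in both arms. All rates below are assumed, and the protocol states no formal test of this count.

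| Assumed true rates | Power, f = 0 | f = 0.2 | f = 0.3 | f = 0.5 |
|---|---|---|---|---|
| 3% vs 6% | 67% | 57% | 51% | 39% |
| 5% vs 10% | 88% | 80% | 74% | 59% |
| 3% vs 13% | over 99% | over 99% | over 99% | 99% |

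The effect runs from negligible to substantial according to inputs the documents do not supply. The table is an illustration, not an estimate.

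**4. Would a longer line fit the existing scheme?** Yes. Other 8.8 items already run to 7, 30 and 90 days. Sections 6.1 and 6.2.2 schedule vital signs every 6 hours to Day 7 or discharge, a standardized cardiac assessment then, and AE forms.

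**The case against.** The strongest reply is that nothing here is a true contradiction. Section 8.2 defines an acute event, while 5.3.1 recommends clinical alertness. A short window for an infusion-related complication can sit beside longer vigilance. The pharmacology in 2.2.2 partly supports it: the albumin rise peaks at 4 hours and is gone by 48-72 hours, and hemodilution is greatest at 4-12 hours, so the window contains the peak exposure. Events in hours or days after dosing are compatible with 48 hours. Respiratory failure and respiratory insufficiency are defined in 8.2 without a time limit, and 30-day mortality is followed with its own stopping guideline (10.7.2). Final safety tables may also be set out in the SAP, which was not available for this review.

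Most of this stands, and it limits the point. It does not remove it, because 5.3.1 itself gives a 7-day oncotic effect as the reason for vigilance, and the definition, SAE rule and monitoring list are fixed in the protocol. The general AE route is also a weaker substitute. Read literally, 8.1 confines adverse events to those not previously identified, or more frequent or severe than previously reported, which could leave out a known complication. The clinical features of pulmonary edema in 8.2 carry no time limit of their own, so a generous reader could apply them later, but the section does not say so.

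Four stronger readings are tempting and not supported.

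- A reader might infer that later episodes are not monitored at all. Sections 8.4, 8.7 and 10.7.3 say otherwise.
- A reader might infer that the cut-off biases the comparison toward no difference. That needs late episodes to cluster in the albumin arm, and nothing in the protocol shows this.
- A reader might apply the Phase I rate of about 13% (section 7.1) to 550 albumin subjects (550 × 0.13 = 71.5) and count a fraction as lost. Section 7.1 says those cases were all mild, whereas the 8.8 CHF item takes only severe or life-threatening ones, and no late share is given.
- A reader might infer that Part 2 exists because of excess deaths in Part 1. Sections 10.2.3 and 10.7.2 say only that those deaths motivated the 30-day safety outcome and its stopping guideline.

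**Conclusion.** The point holds as a modest, cheaply corrected gap. The purpose-built count of the main expected harm covers about 29% (25-32%) of the period that section 5.3.1 associates with albumin's oncotic effect, and the protocol does not reconcile the two. Between about 48 hours and Day 7, an episode has no 8.2 definition or CHF grade, no automatic SAE status and no place in the named by-arm items, although it is still recorded and reported by the general route.

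The number of episodes affected cannot be stated, nor whether the between-arm ratio is distorted. Given the albumin time course, most episodes may well start inside the window. The conclusion rests only on the wording of the sections compared, not on any assumed event rate.

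**What to change.** Reconcile the event window with the 7-day statement.

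- In 8.2, apply the existing definition and grading from randomization through Day 7 or discharge, whichever comes first, and label onset within 48 (±6) hours as the acute sub-period.
- In 8.8, add a by-arm line for pulmonary edema/CHF and one for shortness of breath over the same period, and keep the 48 (±6) hour lines.
- In 8.1, say explicitly whether the trial-specific SAE rule follows the longer window or stays with the acute sub-period.

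This changes how events are classified and tabulated, not how patients are treated. The cost is amendment wording and extra lines in the DSMB tables, since the examinations and forms are already scheduled. The downside is that some cardiac events unrelated to the drug will be counted in both arms, which is a reason to show the two periods side by side rather than replace one with the other.

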7. CLINICAL MANAGEMENT OF ADVERSE EXPERIENCES

7.1 Complications of ALB Therapy

The major concern with ALB therapy is volume overload. ALB has oncotic properties and therefore draws sodium and water into the intravascular space. Subsequently ALB redistributes in total body water. Administration of ALB at higher doses in the Phase I Trial resulted in a 1.5 to 2 g/dL (15-20 g/L) increase in plasma albumin levels at 4 hours post-administration. The overall

incidence of clinical signs of CHF was approximately 13%, but in each case it was mild and the subjects responded to a maximum of 2 doses of furosemide.

Other potential cardiac complications of ALB therapy include atrial arrhythmias (e.g., atrial fibrillation/flutter) and possible myocardial ischemia. Volume infusion may promote atrial wall stress due to stretching, which could lead to atrial arrhythmias. A similar mechanism may occur, causing ischemia. Myocardial wall stress is associated with greater metabolic demand, which may not be available in a subject with coronary stenoses, as many stroke subjects may have. Further, the vast majority of stroke patients are chronic hypertensives, and such patients already tend to have reduced myocardial compliance.

Note that myocardial distress may occur, as shown by evidence of slightly elevated troponins, in up to 20% of ischemic stroke subjects, even without evidence of a true acute coronary syndrome. Thus, it is important to make a clear distinction between subjects who have troponin elevation due to an acute coronary syndrome and troponin elevation without acute coronary syndrome. The latter may be caused by the stroke and is presumed to arise by the same mechanism as seen in acute sub-arachnoid hemorrhage. Stroke may cause a catecholamine surge, possibly due to involvement of the insula, resulting in subendomyocardial damage.

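### The moderate and severe grades of pulmonary edema in Protocol 8.2 overlap, so the trial-specific SAE rule and the by-arm severe CHF count depend on how each site reads them

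*Protocol*

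**What the plan says.** Protocol 8.2 defines acute CHF/pulmonary edema within 48 (±6) hours of randomization and splits it into five grades. Three matter here.

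- **Mild (ii):** the subject responds to the one mandated diuretic dose and needs oxygen by nasal prongs only.
- **Moderate (iii):** "the subject requires more than the mandatory dose of a diuretic but responds and requires supplemental oxygen via nasal prongs only".
- **Severe (iv):** "the subject requires treatment with multiple doses of diuretic, supplemental oxygen via face mask, or additional problems arise such as cardiac arrhythmias", the last item being completed by a need for cardiac telemetry.

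The unit of dose is fixed in the same section: "A single dose of diuretic shall be considered 20mg of intravenous furosemide". Section 5.3.1 sets the mandated dose at the same amount: "A single dose of furosemide, 20 mg IV".

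Two other sections use the grade. Section 8.1 has a rule specific to this trial: severe or life-threatening "pulmonary edema or CHF (as defined in Section 8.2) occurring within 48" (±6) "hours of randomization is considered a SAE". Section 8.8 lists, among the events reviewed by treatment group by unblinded trial personnel and the DSMB, "Severe or life threatening pulmonary edema or CHF within 48" (±6) hours. Neither names the moderate grade.

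**The concern.** Section 7.1 names volume overload as the main concern with albumin, and this scale is how the trial separates a severe episode from a lesser one. If one clinical picture satisfies two adjacent grades, two sites can grade identical subjects differently and both be following the protocol.

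The grade has consequences. Once an event is entered as an SAE it is reported within 24 hours and reviewed by the Medical Safety Monitors (8.5), has a narrative and relationship assessments (8.4), and is followed for up to 12 months (8.1). A non-serious event is followed to the 3-month visit. The severe-or-worse CHF line that the DSMB sees by arm in 8.8 also depends on the grade. At stake is the consistency of that count and of the SAE classification, not the existence of the safety data.

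**Working it through.** The plan gives no figure to reproduce. The check lists the clinical pictures that 8.2 distinguishes and asks which grade each one meets.

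**Inputs, all from 8.2 and 5.3.1**

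- One dose is 20 mg IV furosemide, which is also the mandated dose. Two or more such doses is therefore both more than the mandated dose (grade iii) and repeated dosing (grade iv).
- Oxygen route: nasal prongs or face mask. Ventilatory support belongs to grade (v) and is left out.
- Additional problem (such as arrhythmia with telemetry): no or yes.
- Response to the diuretic is assumed where grades (ii) and (iii) require it. Grade (iv) does not mention response, so response does not take a subject out of severe.

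**Two readings of grade (iv)**

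- Reading 1, as written: repeat doses OR face mask OR additional problem.
- Reading 2, charitable: (repeat doses AND face mask) OR additional problem.

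| Doses | Oxygen | Additional problem | Reading 1 | Reading 2 |
|---|---|---|---|---|
| 1 | prongs | no | mild | mild |
| 1 | prongs | yes | mild and severe | mild and severe |
| 1 | mask | no | severe | **no grade** |
| 1 | mask | yes | severe | severe |
| 2 or more | prongs | no | **moderate and severe** | moderate |
| 2 or more | prongs | yes | moderate and severe | moderate and severe |
| 2 or more | mask | no | severe | severe |
| 2 or more | mask | yes | severe | severe |

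**Result**

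- Under Reading 1, 3 of the 8 pictures meet two grades. Every picture that meets moderate also meets severe, so moderate has no territory of its own.
- Under Reading 2, 2 of the 8 meet two grades and 1 meets none.
- Taking repeated dosing to mean three or more doses does not cure Reading 1. Grade (iii) has no upper limit on doses, so three doses on prongs would still meet both.

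Section 8.2 contains no statement that the highest grade, or any other, takes precedence.

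**Link to the counts**

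For the subject on repeat diuretic and nasal prongs who responds and has no other problem:

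| Site's grade | SAE under the specific rule in 8.1 | In the severe CHF line of 8.8 |
|---|---|---|
| Moderate | no | no |
| Severe | yes | yes |

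Review by the Medical Safety Monitors does not even this out. Under 8.5 they review events already entered as SAEs, so a case that a site grades moderate and non-serious does not reach them by that route.

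**The case against.** The strongest case on the other side is that little turns on this line, and much of that stands.

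- **Moderate cases do not disappear.** A reader might infer that they go unmonitored. The document does not support that. All adverse events are recorded with severity (8.4) and go to the DSMB in aggregate (8.7). Monthly reports give safety data by treatment code (10.7.3). Shortness of breath within 48 (±6) hours is its own monitored line in 8.8 and may capture such a subject.
- **A moderate case is not necessarily a non-SAE.** The general criteria in 8.1, such as prolonged hospitalization or an important medical event, still apply.
- **No formal test uses the grade.** The safety outcome evaluated statistically is 30-day death (10.2.3), and the safety stopping guideline in 10.7.2 uses only that.
- **Phase I does not prove the point.** Section 7.1 says of the Phase I CHF cases that "in each case it was mild and the subjects responded to a maximum of 2 doses of furosemide". A reader might take this as a contradiction of 8.2, where mild means one dose. But the document does not say that Phase I used the 8.2 grades, and it gives neither the milligrams per dose nor the oxygen route. It also plans no comparison of graded CHF rates with Phase I.
- **Each site's reading applies to both arms.** Allocation is blinded and stratified by site (4.3.3), so the ambiguity is not a difference in rule between arms.

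It might also be said that the Manual of Procedures settles the boundary. That manual is not at hand. Section 8.1, however, names 8.2 as the definition, and 8.2 should stand on its own.

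None of this removes the overlap. It limits what the overlap can damage.

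**Conclusion.** The point holds as a flaw in a definition with operating consequences. As written, a subject who needs repeat diuretic, responds and stays on nasal prongs is both moderate and severe. The charitable reading exchanges that overlap for a gap. The trial-specific SAE classification and the by-arm severe CHF count can therefore vary with local reading. If borderline cases arise more often in one arm, the difference between arms on that line would shift with the reading too.

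The size in subjects cannot be derived. A reader might multiply the Phase I rate of clinical CHF signs, about 13% (7.1), by half of the 1,100 subjects: 0.13 × 550 = 71.5, about 72. That is not an estimate of affected subjects. The rate comes from a trial across six dose tiers with treatment up to 16 hours after onset, and it counts clinical signs, not events meeting the 8.2 definition. The share needing repeat diuretic on nasal prongs is not given.

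The conclusion rests on the wording of 8.2, the 20 mg unit, and the absence of a precedence rule in the protocol. It does not touch the efficacy analysis or the mortality guideline. It is worth correcting because it concerns the main expected harm and the correction is cheap.

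**What to change.** Reconcile grades (iii) and (iv) of 8.2 so that every combination of diuretic use, oxygen route and additional problems falls in exactly one grade. The wording should state where repeat diuretic with response on nasal prongs belongs, where one dose with a face mask belongs, and how an additional problem in a nasal-prong subject is graded. The sponsor's clinicians choose the boundary; this review does not propose one.

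A shorter alternative is to state that the highest grade met applies. That removes double grading, but with grade (iv) left as written it would empty the moderate grade, so the choice should be deliberate.

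Section 8.1 already refers to 8.2 and needs no change. Section 8.8 should carry the same cross-reference.

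Regrade cases already reported, blind to arm, under the new wording. Diuretic use has a form in the schedule of assessments (6.1). Oxygen route is not shown as a collected item, since the vital signs in 5.1 name only oxygen saturation, so some cases may need source records.

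The cost is a one-paragraph amendment, one cross-reference and a small amount of blinded record review.
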